4. STUDY POPULATION

4.1 Population (base)

Potential subjects will be recruited via distribution of flyers and publication of the flyer on the intranet of Erasmus MC. .

4.2 Inclusion criteria

In order to be eligible to participate in this study, a subject must meet all of the following criteria:

- Male;
- Healthy;
- 18-75 yrs old.

4.3 Exclusion criteria

A potential subject who meets any of the following criteria will be excluded from participation in this study:

- Allergic for tomatoes;
- Any gastrointestinal disorder within 3 months prior to the intervention;
- Recent medication or supplement use;
- Recent substantial change in weight;
- Adherence to a specific diet (for example the Moorman-diet);
- Using recreational drugs more than once a month;
- Smoking and excessive alcohol consumption (>10 standardized glasses a week).
- Risk of a dependency situation with the researchers.

4.4 Sample size calculation

Observational study obtaining individual lycopene concentration curves in plasma. It is anticipated that a measurable lycopene response will be seen in all participants. Based on the literature described in the introduction section it is hypothesized that in Dutch participants the plasma level of lycopene might be comparable to the Swiss population, that a single dose response to 40mg lycopene in combination with oil will provide a measurable response of plus 10% in all individuals. Therefore a sample size of two times five participants (10 participants in total) has been chosen.

Our pilot still needs to obtain an impression that responses are observed in all individuals, and to confirm that our HPLC-assay is an adequate technique. We will express that in

percentages of the group, such as: 'In xx percent the lycopene concentration increased more than 10% of the T=0 within 48 hours after intervention A'.

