Study design: We have chosen lycopene as it is related to PCa growth, it can be used as a dietary intervention, and it is measurable reproducibly in food and in body fluids. Here we study the lycopene plasma concentration dynamics after a single dose consumption in volunteers in a Dutch setting (which differs from the geographic and environmental setting and life-style in the above mentioned studies). This is to obtain the necessary information on technology, logistics, and food products needed to conduct the follow-up study (METC 2017-389) in cancer patients. Once we have proven that a measurable response can be obtained in healthy volunteers in a Dutch population, that the assay is available and robust, and in line with food consumption as evaluated by validated food questionnaires, we will incorporate that parameter (lycopene) in the current randomised study for men with PCa and undergoing treatment or have undergone treatment in the past in which three dietary interventions are given and compliance to the intervention is currently measured by food intake questionnaires (METC 2017-389).

Here we test plasma lycopene as a candidate compliance marker for that purpose. This is based on the assumption that in Dutch participants the plasma level of lycopene might be comparable to the Swiss population literature, that a single dose response to 40 mg lycopene in combination with oil will provide a measurable response of plus 10 % in individuals, and that a concentration between 1000-1500 nmol/l is appreciated by patients and caregivers as the optimal lycopene plasma concentration to be accomplished long term (1-3 months).

Dietary interventions should always be analysed against the background of the normal individual diet. Therefore, to evaluate the lycopene intervention and related marker, it is

crucial to take the participant's habitual diet, as well as actual food intake during the intervention into account [6].

Research questions:

- 1) Can a plasma lycopene concentration serve as a response parameter after a single dose of dietary lycopene.

We will measure plasma carotenoid concentrations (including lycopene) in response to a single dose dietary intervention with lycopene-rich food or a lycopene tablet in a cross-over study design.

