10.1 Primary study parameter(s)

Lycopene plasma concentration curves over time will be depicted in tables and in graphs in absolute and relative (compared to T0) amounts. Trends in changes over time will be interpreted, if needed based on background information on confounding parameters. There are no statistical calculations planned.

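### Ten men are derived from an assumed response in everyone, and section 10 excludes any calculation, so the responder percentage would carry no interval although 10 of 10 leaves up to 30.8% non-responders (exact two-sided 95%)

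*Protocol*

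**What the plan says.** Section 4.4, headed as a sample size calculation, hypothesises that a single 40 mg dose with oil "will provide a measurable response of plus 10% in all individuals". The next sentence reads: "Therefore a sample size of two times five participants (10 participants in total) has been chosen". No confidence level, power, standard deviation, target precision or minimum responder rate is given.

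The same section describes the purpose modestly: "Our pilot still needs to obtain an impression that responses are observed in all individuals". It plans to express this as a percentage of the group and gives as its example the share of men in whom "the lycopene concentration increased more than 10% of the T=0 within 48 hours after intervention A".

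For the primary parameter, section 10.1 plans display only: "Lycopene plasma concentration curves over time will be depicted in tables and in graphs in absolute and relative (compared to T0) amounts". It closes with "There are no statistical calculations planned". The same exclusion stands in the opening of section 10 and in 10.2 and 10.3.

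Section 1 says what the pilot is for. The marker will be incorporated in the current randomised prostate cancer study "Once we have proven that a measurable response can be obtained in healthy volunteers in a Dutch population", with two further conditions: "that the assay is available and robust, and in line with food consumption as evaluated by validated food questionnaires".

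**The concern.** The word that links assumption to sample size in section 4.4 supports nothing. If every man is assumed to respond, any number of men would be consistent with that assumption, so it cannot lead to ten.

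The protocol also describes the strength of its evidence in two ways. Section 1 says proven and section 4.4 says impression. The percentage meant to carry that evidence would come with no statement of uncertainty, because sections 10 to 10.3 rule out calculation. This is a stated choice, not a detail left to an analysis plan that is not shown.

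A compliance marker is read man by man, so the fraction of men who do not respond is the quantity of interest. The protocol itself gives reasons to expect some:

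- Section 1 says genetic variants may partly explain heterogeneous blood responses.
- Section 1 also allows that a high habitual intake may leave little response to a single dose.
- Section 13.1 calls the changes in plasma carotenoids unpredictable.

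At stake is how much the marker decision can rest on a count out of ten. A bare 100 percent can be over-read.

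**Working it through.** **Inputs from the protocol.** There are ten men, five per sequence (sections 3 and 4.4). In the cross-over each man takes both products, so n = 10 per product. A responder is a man whose concentration rises by more than 10% of T0 within 48 hours (the example in 4.4).

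**Assumption of this review.** The confidence level is 95%. The protocol gives none. Two-sided limits are the main figures, with the one-sided bound shown as a variant.

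**Step 1: the plan's own figure.** n = 10 cannot be reproduced. Without a level, power, spread, target precision or minimum rate, no standard formula applies.

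**Step 2: precision of the planned percentage.** Exact (Clopper-Pearson) limits for x responders out of n:

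- lower limit = 0.025 quantile of Beta(x, n − x + 1)
- upper limit = 0.975 quantile of Beta(x + 1, n − x)

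For x = n the lower limit reduces to 0.025^(1/n). With n = 10 this is 0.025^(0.1) = 0.692, so non-responders could be as many as 1 − 0.692 = 0.308. The one-sided 95% bound is 1 − 0.05^(0.1) = 0.259.

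| Responders | Exact two-sided 95% interval for the response rate |
|---|---|
| 10/10 | 69.2% to 100% |
| 9/10 | 55.5% to 99.7% |
| 8/10 | 44.4% to 97.5% |

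Other methods agree closely for 10/10. The upper limit for non-responders is 27.8% by Wilson (two-sided) and 3/10 = 30% by the rule of three.

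**Step 3: how often 10/10 is seen when not everyone responds.** P(10/10) = p^10 for a true response rate p:

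| True rate | P(10/10) |
|---|---|
| 95% | 0.95^10 = 0.60 |
| 90% | 0.90^10 = 0.35 |
| 80% | 0.80^10 = 0.11 |

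**Step 4: if men are lost.** Section 8.5 replaces only men who withdraw before T0 and reconsiders new participants at ten minus three. If seven remained and all seven responded, up to 1 − 0.025^(1/7) = 0.410 could still be non-responders.

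**The case against.** The strongest reply is that this is a declared descriptive pilot. Such a study may take ten men without a power calculation. Section 4.4 promises an impression and percentages of the group, which describe the ten men studied. The individual curves will be shown, and any reader can see that n is ten. This largely stands. Ten men is an acceptable choice, and the point does not ask for more.

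Several stronger readings are tempting, and the protocol does not support them:

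- **That all men must respond before the marker is used.** Section 1 requires only that a measurable response can be obtained. That is a claim of existence. The aim of seeing it in all individuals belongs to section 4.4.
- **That the responder percentage alone decides adoption.** Section 1 adds the assay and questionnaire conditions.
- **That the result will be overstated.** This predicts how a report will be written. The text supports only that a bare percentage can be over-read.
- **That 10/10 is the likely result when a material minority does not respond.** At true rates of 90% and 80% the probabilities are 0.35 and 0.11. It is possible at both, and more likely than not at neither.
- **That compliant men in the follow-up study would be labelled non-compliant.** Section 1 says compliance is currently measured by questionnaires and that lycopene would be incorporated. It does not say that a man will be judged on a single-dose rise of 10%.

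The reply does not remove the unsupported step from assumption to sample size, the express exclusion of any calculation, or the mismatch between proven and impression.

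**Conclusion.** The point holds as one of precision and wording. Section 4.4 gives no quantitative basis for ten men. The best possible result, 10/10, would be compatible with up to 30.8% non-responders (exact two-sided 95%; 25.9% with a one-sided 95% bound). It therefore cannot by itself support a statement about all individuals beyond the ten, and the protocol plans nothing that would show this limit.

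The figures rest on the assumed 95% level, on the responder definition given as an example in section 4.4, and on all ten men contributing to each product. With fewer men the interval widens. The point does not make the design invalid, and it does not show that the pilot's descriptive aim is out of reach. It limits what the pilot can be said to have established.

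**What to change.** 1. **Section 4.4.** Replace the sentence that derives the sample size with a statement of feasibility and precision, for example: *Ten men were chosen for feasibility. If 10 of 10 respond, the exact two-sided 95% interval for the response rate is 69.2% to 100%; if 9 of 10 respond, it is 55.5% to 99.7%.*
2. **Sections 10 and 10.1.** Replace the exclusion of calculations with: *For each product, the percentage of men with a rise above 10% of T0 within 48 hours will be reported with its exact 95% confidence interval.* Align 10.2 and 10.3, where the same exclusion appears, so that they do not contradict this.
3. **Sections 1 and 4.4.** Reconcile proven with impression, for example by writing *found feasible* in section 1.

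The cost is a few sentences and a few lines of analysis. No extra men, visits or samples are needed. The claim that the pilot can make becomes less favourable.

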While the generally accepted opinion is that diets high in antioxidants are beneficial for suppressing and prevention of all cancers, and that they promote the overall health status of individuals, it may be difficult to change a life style that incorporates a healthy diet. Therefore in this study, we are searching for a parameter in body fluids that reflects the intake of healthy diet, and as such may motivate and sustain its continuous use (compliance marker). In case of prostate cancer we address lycopene as our target for reasons described above. Ideally, our lycopene related marker should reflect the short-term uptake of lycopene, and be based on a single dose consumption, in order to act as a direct feed-back to the consumers dietary action. Current methods of determination (see further) do not yet live up to point-of-care applications. There is, however, evidence that single dose consumption is reflected in the lycopene plasma concentration. In a trial in Italian consumers on lycopene kinetics on single dose consumption [5], a significant increase of plasma lycopene concentration of 40

nmol/l was observed above an individual base level (around 400 nmol/l), with a max concentration at 12 hours, and a normalisation after 48 hours after consumption of 15 mg of lycopene. Also a biomarker reflecting the adequate lycopene consumption of a medium long term (e.g. one week consumption) might provide a valuable asset for consumers. In a trial in Swiss male consumers on an 8-day intervention of 20 mg after lycopene depletion, the individual lycopene plasma concentration topped to a steady state of 1000 to 1500 nmol/l, while two weeks after the intervention (so during lycopene depletion) a plateau phase was obtained on a plasma concentration of 400-500 nmol/l [4], likely due to the release of lycopene from liver resources. We conclude that for consumer reasons the choice for a point-of-care testing of single dose lycopene is feasible, but restricted by current technology, and that feed-back on medium long term lycopene consumption is also feasible, as it is well reflected in plasma lycopene concentrations.

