Plasma lycopene concentrations show variation between individuals, and within individuals. It is unknown if and how much a single dietary intervention with lycopene from lycopene-rich vegetables like tomatoes alters the plasma concentration, and therefore can be used as a compliance marker.

As the bioavailability and plasma kinetics of lycopene is known to a limited extend (see studies above), a scheme for plasma determinations is followed according to previous marker (GABA, also found in tomatoes, serving as an exemplary study design) research from the same Wageningen group, including a wash out period of at least two weeks between interventions in the cross-over design [7].

- 2) Is a tablet lycopene with equivalent lycopene content as effective as a single dose dietary intervention regarding the change of plasma lycopene concentration?

Previous studies suggest equivalence, which might be of interest for consumers/patients.

- 3) Is the prior food consumption of individuals, as measured by dietary questionnaires, related to the plasma lycopene levels before and after lycopene intervention?

If an existing individual high intake of lycopene as analysed by a validated questionnaire would result in a high standard plasma lycopene concentration, or little response on single dose lycopene consumption, the subject might exclude for further supplementary lycopene consumption and life style changes.

Intervention: We have chosen a single dose of 40 mg lycopene as an intervention based on the following. Previously, in a dose escalating study to 90 mg lycopene daily in men with Research protocol

recurrent PCa after primary treatment, no effects were seen on the level of PSA, in contradiction to two studies conducted in men with metastatic PCa [8]. Also in high doses maintained for several weeks no toxicity was observed, while lycopene plasma levels corresponded with dietary dose. For chronic use, the daily dose of 30 mg is recommended based on a large review [9].

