3. STUDY DESIGN

Cross-over interventional pilot study.

Ten healthy individuals (male 18-75 years) are randomly divided in two groups (A and B) of 5 individuals. One week before the dietary intervention a daily food questionnaire will be completed.

One hour before the intervention a blood sample will be taken (all blood samples 6 ml EDTA plasma tube). All individuals will be given an infusion needle for 26 hours. Samples are spun and plasma is pipetted and distributed over 1 ml Eppendorf cups for immediate freezing at -80 Celsius at the research lab.

Group A will take 40 mg lycopene (2,5 pills of food supplement Vitabiotics Ultra Lycopene 15mg, potent extract). Group B will take 250 ml of tomato soup (matching with 40 mg lycopene) with 20 ml olive oil. Blood sampling as described in all individuals from needle: 1,3,6,12,24 hours after intervention, and after 48 and 72 hours by direct venapunction. Wash out period of 3 weeks, after which the identical above procedure takes place including questionnaires, but group A and B changed (cross-over). All samples (n=160) will be frozen at -80, and transported on dry ice to Wageningen University for lycopene determination.

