8. METHODS

8.1 Study parameters/endpoints

8.1.1 Main study parameter/endpoint

Raise of plasma lycopene concentration in absolute (ng/ml) and relative (percentage of T0-value) after single lycopene intervention.

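### Section 4.4's example response percentage (more than 10% above a single T0) is tied to no noise figure and cannot by itself show that the assay is adequate; report the assay CV and the noise-only rate beside it

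*Protocol*

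**What the plan says.** Section 4.4 hypothesises "a measurable response of plus 10% in all individuals" after 40 mg. It gives the pilot two aims: to see whether all men respond, and "to confirm that our HPLC-assay is an adequate technique". It commits to expressing these as percentages of the group and offers one sentence as an example: "In xx percent the lycopene concentration increased more than 10% of the T=0 within 48 hours after intervention A". No other numeric cut-off for the single-dose response appears in the protocol.

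Section 3 fixes the sampling. There is one pre-dose sample per period ("One hour before the intervention a blood sample will be taken"), followed by samples at "1,3,6,12,24 hours after intervention, and after 48 and 72 hours by direct venapunction". Six of the seven post-dose samples fall within 48 hours.

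Section 1 accepts that "Plasma lycopene concentrations show variation between individuals, and within individuals", without a figure. It also cites a single-dose study of 15 mg in which a rise of 40 "nmol/l was observed above an individual base level (around 400 nmol/l), with a max concentration at 12 hours". Sections 1 and 8.3 plan a pooled plasma sample in duplicate in every analytical batch for quality control, but do not link it to the 10%.

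The main endpoint in section 8.1.1 is "Raise of plasma lycopene concentration in absolute (ng/ml) and relative (percentage of T0-value) after single lycopene intervention". Section 10 plans tables and graphs of the curves and no statistical calculations.

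**The concern.** A responder percentage depends on three things: the true rise, the cut-off, and the noise in the values compared. Section 4.4 sets the cut-off equal to the rise it expects and leaves the noise out.

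Three consequences follow. First, a man who behaves exactly as hypothesised sits on the cut-off, so whether he is counted is close to a coin toss even with a precise assay. Second, comparing the best of six samples with one T0 gives noise six chances to pass the bar, and one low T0 helps all six. Third, where the true rise is 10% or less, a noisier assay makes the percentage larger, so a high percentage is not evidence of a good assay.

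What is at stake is how one summary figure is read. Section 1 says lycopene will enter the running study in men with prostate cancer once a measurable response and a robust assay have been shown. With 10 men per intervention, each man wrongly counted or missed moves the percentage by 10 points.

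**Working it through.** **Figures from the protocol.** Cut-off: +10% over T0. Pre-dose samples per period: 1. Post-dose samples up to 48 h: 6 (1, 3, 6, 12, 24, 48 h). Men: 10. Cited rise: 40/400 = 10% after 15 mg, which matches the cut-off. The sample size of 10 cannot be re-derived, because no error rate, SD or precision target is given; this point does not dispute it.

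**Assumptions.** The protocol states no CV. The total CV per sample (assay plus within-person) is taken as 2, 3, 5, 7.5 or 10%. Errors are lognormal with log-scale SD s = √ln(1 + CV²). The seven samples share a common correlation ρ of 0, 0.5 or 0.8. Variation shared by T0 and the later samples cancels in the ratio, so ρ acts by replacing s with s√(1 − ρ).

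**One pre-named sample, no true response.** P = 1 − Φ[ln 1.10 / (s√2)] for ρ = 0. At CV 5%, s = 0.04997 and 0.09531/(0.04997 × 1.4142) = 1.349, so P = 8.9%. Over the CV grid P is <0.1, 1, 9, 18 and 25%.

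**Best of six against the shared T0, no true response** (simulation, 1,000,000 draws per setting):

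| CV | ρ = 0 | ρ = 0.5 | ρ = 0.8 |
|---|---|---|---|
| 2% | 0.2% | <0.1% | 0% |
| 3% | 6% | 0.4% | 0% |
| 5% | 29% | 12% | 0.7% |
| 7.5% | 49% | 32% | 9% |
| 10% | 60% | 47% | 23% |

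At CV 5% and ρ = 0, ten men with no response would yield about 10 × 0.29 = 2.9 counted as responders. With independent errors, a +10% cut-off gives a 5% false count only if the CV is about 2.9% (best of six) or 4.1% (one named sample).

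**True peak exactly +10%.** At the 12 h sample alone, P(observed > 10%) = 50% whatever the CV, by symmetry on the log scale. For best of six, assume true rises of 0, 2.5, 5, 10, 5 and 0% at the six times (peak at 12 h and back to normal at 48 h, as in the cited study). At ρ = 0 the man is counted with probability 0.51, 0.55, 0.63, 0.70 and 0.735 across the CV grid. At CV 5% this is 0.57 for ρ = 0.5 and 0.52 for ρ = 0.8. At CV 2% and ρ = 0.8 it is 0.50.

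**Larger true peak.** Scaling linearly from 15 to 40 mg, an assumption, gives 10% × 40/15 = 27%. Such a man is counted about 92% of the time or more at every CV.

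**Precision of the noise estimate.** With k duplicate pairs the assay SD has k degrees of freedom, and its 95% limits are the estimate times √(k/χ²). That gives factors of 0.60–2.87 for 4 pairs, 0.70–1.75 for 10 and 0.77–1.44 for 20. The number of batches is not stated. With 10 pairs and an estimated CV of 5%, the limits are 5% × 0.70 = 3.5% and 5% × 1.75 = 8.75%. The same simulation at ρ = 0 then puts the noise-only rate between about 11% and 56%.

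**The case against.** The strongest reply is that the sentence is an illustration with a placeholder, in a pilot that seeks an impression. The main endpoint is the rise itself, the curves are tabulated and plotted, and a reader can see an isolated spike. Pooled-plasma duplicates are already planned, and section 4.4 does not say that the percentage alone must prove the assay. Whether noise matters is also undetermined: with a CV of 3% or less, or with mostly shared variation, false counting is small, and a peak near +27% would be caught almost always. All of this stands, and it makes the point minor.

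It does not remove the point. The commitment to express both aims as percentages is firm, even though the wording is an example. Nothing in the document links the planned duplicates to the 10% or names them as the evidence for assay adequacy.

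Four stronger readings are tempting and are not supported:

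- That the percentage is a go/no-go rule. No text makes it one.
- That most counted responders would be false. This would need a CV, and the protocol gives none.
- That the protocol contradicts itself on which sample counts. The phrase about 48 hours is naturally read as any sample up to then; at most it is ambiguous.
- That 10% should give way to a noise-calibrated cut-off. At CV 5% such a cut-off (95th percentile of the best-of-six rise from noise alone) is about +18% at ρ = 0 but only +7.5% at ρ = 0.8. It is below 10% in 6 of the 15 CV-by-correlation settings, and the correlation is unknown.

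**Conclusion.** The point holds as a minor one. Section 4.4's example percentage uses a cut-off equal to the expected response and tied to no noise figure, so by itself it cannot show that the assay is adequate, and it is an uncertain guide to whether all men respond. A man with a true peak of exactly +10% is counted about 50% to 73% of the time. A non-responder is counted 0% to 60% of the time over the assumed grid.

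These sizes rest on assumed CVs, an exchangeable correlation, lognormal errors and, for the +10% case, an assumed time profile. The low end of the non-responder range is as compatible with the protocol as the high end. Neither the sample size nor the design needs to change.

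**What to change.** In section 4.4, keep the percentage above 10% and add three statements:

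1. The highest value at 1 to 48 h is compared with T0, for each intervention.
2. The assay CV, with 95% limits, is reported from the pooled-plasma duplicates as the separate evidence for assay adequacy. From k pairs with log difference d, s = √(Σd²/2k).
3. Beside each percentage, the share of non-responders that noise alone would place above +10% under the same best-of-six rule is given. It is calculated with the assay CV, which is a lower bound because it omits biological variation. As a rough sensitivity value, it is also calculated with the CV from each man's two T0 samples.

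The T0 value is only rough: it includes three-week drift and possible carry-over, yet may miss meal-related variation after dosing. Do not add a single calibrated cut-off, because it depends on an unknown correlation and would be imprecise with few duplicates.

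The cost is a little extra descriptive analysis and an amended sentence in section 10, which now says that no calculations are planned. The noise rate will itself be imprecise and should be shown with its range. No new blood draws, participants or data are needed.

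### The main endpoint is a continuous rise in plasma lycopene, but no group estimate of that rise with its uncertainty is planned, and the one group number named is hard to read alone

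*Protocol*

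**What the plan says.** - **Endpoint (section 8.1.1):** "Raise of plasma lycopene concentration in absolute (ng/ml) and relative (percentage of T0-value) after single lycopene intervention". No time point or curve summary is named.
- **Display (section 10.1):** "Lycopene plasma concentration curves over time will be depicted in tables and in graphs in absolute and relative (compared to T0) amounts". Trends are then interpreted.
- **Calculation (section 10.1):** "There are no statistical calculations planned". The same sentence stands in the opening of section 10 and in 10.2 and 10.3.
- **Group result (section 4.4):** the pilot's impression of response is to be given in "percentages of the group, such as" the following: "In xx percent the lycopene concentration increased more than 10% of the T=0 within 48 hours after intervention A".
- **Hypothesis and size (section 4.4):** a 40 mg dose with oil "will provide a measurable response of plus 10% in all individuals", and from this "Therefore a sample size of two times five participants (10 participants in total) has been chosen".
- **Timing (section 1):** the cited single-dose trial is described "with a max concentration at 12 hours, and a normalisation after 48 hours after consumption of 15 mg of lycopene". The optimal time point of the response is itself the first secondary endpoint (section 8.1.2).

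**The concern.** Section 1 makes this pilot a gateway: lycopene enters METC 2017-389 as a compliance parameter once a measurable response has been shown. That decision turns on how large the rise is, how precisely ten men determine it, and how much men differ. A responder share gives none of these. A man at +11% counts the same as one at +60%, and a man at +9% counts the same as one who did not change.

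Two features make the share harder to interpret. The cut lies exactly on the hypothesised effect, so a man whose true peak is +10% falls below it about half the time at his peak sample. In the other direction, the example lets a man qualify at any time within 48 hours, which gives random variation several chances to create a responder.

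A statistical analysis plan may exist that is not at hand. The point does not depend on it, because the protocol does not leave the calculation open but states that none is planned.

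**Working it through.** **Inputs from the protocol.** Ten men; cut at +10% over T0; six samples after intake up to 48 h (1, 3, 6, 12, 24, 48 h); hypothesised rise +10%. The cut agrees with the single-dose source in section 1: 40/400 nmol/l = 10%. The sample size of 10 cannot be reproduced, because no SD, alpha, power or precision target is given.

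**Assumptions (not in the protocol).** Independent log-normal error in every sample including T0, with a total within-man CV of 3%, 5%, 7.5% or 10%. Under a rise, the log-scale shape at the six times is 0, 0.1, 0.5, 1, 0.7, 0.2 times ln(1.10).

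**1. Responders produced by noise.** For one time point and no true rise, P(responder) = 1 − Φ(ln 1.10 / (σ√2)), with σ² = ln(1 + CV²). At CV 5%, σ = 0.0500, so ln 1.10 / (σ√2) = 0.0953 / 0.0707 = 1.35 and P = 8.9%. When any of six samples may qualify, all six share the same T0, so the probability was simulated:

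| CV | No true rise, any of six samples | True +10% at 12 h, any of six samples |
|---|---|---|
| 3% | 6% | 58% |
| 5% | 29% | 65% |
| 7.5% | 49% | 71% |
| 10% | 60% | 75% |

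At CV 7.5%, a report that about 70% responded would have to be read against about 49% from noise alone.

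**2. What the share says about size.** The exact 95% interval is 69.2% to 100% for 10/10, and 44.4% to 97.5% for 8/10. If all ten respond, as section 4.4 anticipates, magnitude is left open. With an assumed SD of 10 points between men, the chance that all ten exceed +10% is Φ((m − 10)/10)^10. This is 0.79 at a mean rise m of 30%, 0.99 at 40% and about 1.00 at 60%.

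**3. Information kept by the cut.** For a normally distributed rise, the share keeps φ(c)²/[p(1 − p)] of the information on the mean, with c = Φ⁻¹(p) and p the response rate. This gives 64% at p = 0.5, 49% at 0.8 and 34% at 0.9.

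**4. What an estimate would deliver.** The 95% half-width for a mean of ten within-man differences is t(0.975; 9) × SD/√10 = 2.262 × SD/3.162 = 0.715 SD. For assumed SDs of 5, 10, 20 or 30 percentage points it is ±3.6, 7.2, 14.3 or 21.5 points.

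**5. Fair comparison at one time point.** The protocol plans no test, so power serves only as a yardstick (one-sided 2.5%, true +10% at 12 h, cut and paired log mean both taken at 12 h):

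| CV | Cut, no between-man SD | Paired mean, no between-man SD | Cut, 5% between-man SD | Paired mean, 5% between-man SD |
|---|---|---|---|---|
| 3% | 99% | 100% | 99% | 98% |
| 5% | 83% | 96% | 82% | 87% |
| 7.5% | 62% | 72% | 62% | 63% |
| 10% | 38% | 48% | 37% | 43% |

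At CV 5% to 10% the gain is 10 to 13 points when men do not differ. With 5% between-man SD it is about 0 to 6 points.

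**The case against.** The strongest reply is that descriptive reporting is a legitimate and openly stated choice in a ten-man pilot. A personal compliance marker needs the individual question answered, since a convincing mean could hide several men who do not respond. Both points stand: the percentage should stay and no hypothesis test is called for.

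Three stronger readings are tempting, and the documents do not support them.

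- **The size of the rise is lost, or most of the information is discarded.** Section 10 tabulates and plots the curves on both scales of section 8.1.1, so size and spread can be read from the tables. The loss concerns the group summary only. It exceeds half only when about 80% or more respond; at 50% it is 36%.
- **The percentage replaces the continuous endpoint.** It is introduced as an example, in the sample-size section, and serves an individual-level aim. What remains is that no other group summary is named and section 10.1 excludes calculating one.
- **Dichotomising costs about half the power.** At CV 5%, the any-of-six-samples share has 52% power against 96% for the paired mean at 12 h. That contrast changes two things at once, a best-of-six rule against one pre-chosen time. The like-for-like gain is the modest one shown above, and it shrinks further for larger effects: with a true +20% rise (assumed), cut and mean at 12 h differ by at most about 5 points.

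A further objection is that a 12 h headline borrows its timing from a 15 mg study, while the timing of the response is a secondary endpoint here. That is correct. If men peak at different times, a 12 h mean loses power, so 12 h can only be a labelled assumption.

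**Conclusion.** The point holds in a limited form. The protocol collects a paired continuous measure and displays it fully, but it rules out any group estimate of the rise with its uncertainty. The one group number it names sits on the hypothesised effect and may be inflated by noise: about 6% to 60% of men would count as responders with no true rise, over assumed CVs of 3% to 10%. These rates rest on independent log-normal error and on reading the example as allowing any of six samples. They do not describe a cut applied at one time.

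The main benefit of a change is an estimate of size and spread for the decision on METC 2017-389. The gain in sensitivity over a single-time cut is secondary and can be nil. This is a cheap improvement that should be made; it does not invalidate the pilot.

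**What to change.** In section 10.1, and in the opening of section 10 so that the two agree, replace the sentence excluding calculations for the primary parameter with the following:

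- For each product and every sampling time, report the geometric mean ratio to T0 and the mean absolute rise. Give each a 95% confidence interval from the ten within-man differences (on the log scale for the ratio), and add the between-man SD.
- Name one headline summary in advance. Examples are the 12 h ratio, labelled as an assumption taken from the 15 mg single-dose source, or a baseline-corrected area under the curve, which depends less on the exact peak time.
- Keep the share above +10% as the individual-level description.
- State that no hypothesis test is planned.

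The cost is a few lines of text and one small table from the 160 samples already planned (2 periods × 8 times × 10 men), with no extra visits or participants. The downside is that a headline must be chosen beforehand and may miss the true peak; reporting all times limits that.
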